8.2.2 Aqueous Solubility

As per package insert.

8.2.3 Packaging and Labeling

Fulvestrant is commercially available.

8.2.4 Storage Conditions

As per package insert.

8.2.5 Stability Data

As per package insert.

8.2.6 Handling and Drug Accountability

As per institutional guidelines.

8.3 ^{18}F -FFNP

8.3.1 ^{18}F -FFNP Description

The chemical name of ^{18}F -FFNP is 21-[^{18}F] fluoro-16 α ,17 α -[(R)-1'- α -furylmethylidene) dioxy]-19-norpregn-4-ene-3,20-dione. ^{18}F -FFNP is a radiolabeled progestin analog that binds to progesterone receptor with high affinity and selectivity (7-9). In primary and metastatic breast cancer, uptake of ^{18}F -FFNP measured by PET/CT imaging has been shown to correlate with PR expression in biopsy material assayed by immunohistochemistry. ^{18}F -FFNP is primarily cleared from the body via hepatobiliary elimination.(50-54)

8.3.2 Packaging and Labeling

^{18}F -FFNP is not currently commercially available. cGMP-grade ^{18}F -FFNP will be manufactured on site in the UW-Madison Radiopharmaceutical Production Facility. This facility has been qualified and approved for production by the NCI Cancer Imaging Program and ECOG-ACRIN for clinical trials using other investigational radiopharmaceuticals, such as ^{18}F -fluoroestradiol and ^{18}F -fluorothymidine. Specific manufacturing processes will follow our approved Drug Master File for ^{18}F -FFNP. The investigational pharmacist or qualified nuclear medicine technologist will be the responsible party designated by the investigator.

^{18}F -FFNP is synthesized with high specific activity so the quantity of progestogenic material injected with the radiopharmaceutical is < 7 μg (<16.3 nmol). The final ^{18}F -FFNP product solution contains 90% (v: v) USP 0.9% sodium chloride injection and 10% (v:v) USP ethanol alcohol injection. Up to 10 mL of ^{18}F -FFNP may be administered for a single PET scan.

The injected dose of ¹⁸F-FFNP will be approximately 7 mCi (259 MBq) with a specific activity greater than 200 Ci/mmol.

¹⁸F-FFNP is the only active ingredient. There is no evidence that nonradioactive and radioactive FFNP molecules display different biochemical behavior.

8.3.3 Storage Conditions

In accordance with regulations, the radiopharmaceutical facility conducts several quality control tests on the ¹⁸F-FFNP product prior to release for human administration. Once delivered, doses will be stored in the appropriate storage area in the nuclear medicine facility until they are administered to the subject.

The drug solution is stored at room temperature in a gray butyl septum sealed, sterile, pyrogen-free glass vial.

8.3.4 Stability Data

The expiration time of ¹⁸F-FFNP is six hours.

8.3.5 Handling and Drug Accountability

The investigator is fully responsible for the investigational products at the trial site. Dispensing of investigational products will be delegated to site staff. The investigational pharmacist or qualified nuclear medicine technologist will be the responsible party designated by the investigator. The person responsible for dispensing the investigational products will be responsible for maintaining adequate control of the investigational products and for documenting all transaction with them.

9 STATISTICAL CONSIDERATIONS

9.1 Study Design

This is a single-arm phase II clinical trial to determine the efficacy and monitoring the safety of treatment with fulvestrant plus onapristone with ER-positive, (PgR-positive or PgR negative), HER2-negative locally advanced or metastatic breast cancer, which progressed on or after treatment with an endocrine therapy and a CDK4/6 inhibitor.

Tumor response to treatment will be based on RECIST 1.1 criteria using local radiological assessments. Subjects will be treated until disease progression, unacceptable toxicity, or discontinuation from the study treatment for any other reason. A total of 39 patients will be enrolled.

9.2 Sample Size

The sample size calculation for the fulvestrant and onapristone combination arm are made using Simon Two-Stage design (Simon 1989). Using a 5% non-inferiority margin, the ORR rate of 7% or lower will be considered unacceptable as the third-line treatment. The following Simon's design controls type 1 error at 5% (recommending the combination for phase III if the true ORR = 7%) and type 2 error at 20% (NOT recommending the combination for phase III if the true ORR = 20%).

A total of 39 patients will be enrolled, and the study will be conducted in two stages.

Stage I – 21 Subjects

If ≤ 1 response was observed, then the combination of fulvestrant and onapristone will be not considered an active treatment in this group of patients, and the trial will be terminated.

If ≥ 2 responses were observed, then 18 additional subjects will be enrolled.

Stage II – 18 Additional Subjects

If ≤ 5 of 39 responses were observed, then the combination of fulvestrant and onapristone will be not considered an active treatment in this group of subjects, and the study will be terminated.

If ≥ 6 of 39 responses were observed, then the activity of fulvestrant and onapristone will be considered sufficient to launch a phase III clinical trial.

This design yields a one-sided type I error rate of 5% if the ORR is 7%, and power of 80% when the true response rate of the combination is 20%.

Safety monitoring: To prevent exposing more than one-third of enrolled subjects to high levels of adverse events or severe adverse events leading to discontinuation of the combination, the following sequential procedure will be used. If the number of such discontinuation events is higher than three of the first 11 subjects, 4/21, 5/30, and 7/39 [sequential stopping boundaries for (1) 33% rate of discontinuation at a <5% chance of not stopping the study early and (2) 10% rate of discontinuation at a <10% chance of stopping the study early], the principal investigator and study chair will meet to discuss early termination of the study.

Point and 95% interval estimate of ORR will be evaluated accounting for possibility of early futility stopping as describe in Koyama T et al. 2008.(55)

PSF will be described with Kaplan-Meier (KM) Curve and its pointwise asymptotic 95% confidence bounds. Median PFS if reached will be extracted from this KM estimator. Parametric forms (such Weibull) of survival probability will be fitted to the collected data.

[figure not shown]
DCR will be estimated with relative frequency and exact two-sided 95% binomial confidence interval. Time from registration to first documented response (CR or PR) will be evaluated with a cumulative incidence where death will be as a competing risk to response.

Duration of response will be assessed for a subgroup of subjects with observed response. The date of response will be denoted as time zero and time to progression or death will be evaluated with KM curve and 95% CI. Median time to response will be extracted from this KM curve.

The impact of possibility of early stopping due to futility will be evaluated under plausible parametric models using Monte-Carlo simulations with 10,000 repetitions under each plausible scenario.

Type, frequency and severity of adverse events will be summarized with descriptive frequency tables.

Figure 7 Minimax Simon Two-Stage Design Enrolling 39 Subjects

Secondary analyses: Regression analysis will be completed using Cox proportional regression model for PFS and logistic regression model for ORR. Due to a relatively small number of patients in the study, we will investigate the impact of categorical variable if the number of events (responses for ORR and progression or death for PFS) is greater than five per category. The impact of the following predictors will be explored: age, race, ER status, PgR status, prior therapy (type of therapy AI or SERMs such as tamoxifen alone or CDK4/6+endocrine therapy combo), number of metastatic sites, measurable disease, and biomarkers. Single-predictor models will be used. The possibility of multiple Cox and logistic regressions will be considered as well, but due to a small number of patients we are not expecting to fit multiple regressions.

All planned data analyses will be completed with SAS 9.4. Monte-Carlo simulation studies will be completed in R v3.5.1.

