2 HYPOTHESIS AND OBJECTIVES

Table 3 Objectives and Endpoints

Objective	Endpoint
Primary	
Estimate the objective response rate (ORR).	Best overall response of CR or PR, as per RECIST 1.1.
Secondary	
To evaluate progression-free survival rate (PFS).	Time from date of enrollment to the date of first documented disease progression or death due to any cause.
Estimate the disease control rate (DCR).	Best overall response of CR, PR or SD lasting for \geq 24 weeks, as per RECIST 1.1.
To describe time to response and duration of response.	Time to response: Time from enrollment to first documented response (CR or PR). Duration of response: Time between the first date of documented response to progression or death due to breast cancer.
To evaluate the safety and tolerability.	Type, frequency and severity of adverse events and laboratory abnormalities according to CTCAE version 5.0.

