5.3 Discontinuation of Study Treatment, Withdrawal, and Compliance

Discontinuation from the study treatment does not mean discontinuation from the study. Subject will be considered in follow-up, study procedures should still be completed as indicated by the study protocol, and AEs/SAEs will continue to be reported according to this protocol.

In the absence of treatment delays due to adverse events, study treatment/intervention may continue until:

- Disease progression.
- General or specific changes in the subject's condition renders the subject unacceptable for further treatment in the investigator's judgment.
- Intercurrent illness that prevents further treatment administration.
- Subject decides to withdraw from the study.
- The subject has significant noncompliance with the protocol (see below).
- Unacceptable adverse event(s) and/or dose level reduction beyond requirements as detailed in this protocol.
- Study stopping rules are met.

Subjects who sign the informed consent form, enroll, and receive the study intervention, but subsequently withdraw, or are withdrawn or discontinued from the study will not be replaced.

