10.2 Response Evaluation

Imaging assessments for response evaluation will be performed every eight weeks (± 7 days) during the first 12 months and every 12 weeks (± 14 days) thereafter. Additional imaging assessments may be performed at any time as clinically indicated. This schedule should be followed until radiological progression is documented, irrespective of compliance to treatment, or until the subject enters follow-up.

Each lesion that is measured at baseline must be measured by the same method and the same local radiologist throughout the study.

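### Time to response names only death as a competing event and leaves unsaid how subjects who progress without responding are handled; if they are censored, the curve overstates the proportion responding.

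*Combined protocol and SAP*

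**What the plan says.** Section 9.2 states that time from registration to first CR or PR "will be evaluated with a cumulative incidence where death will be as a competing risk to response". Table 3 in Section 2 defines the endpoint but gives no rule for subjects who progress first and no censoring rule. Neither does any other section.

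Three other provisions bear on the point:

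- Section 9.1: "Subjects will be treated until disease progression, unacceptable toxicity, or discontinuation from the study treatment for any other reason". Section 5.3 also lists progression among the reasons to stop treatment.
- Section 10.2, on the imaging used for response: "This schedule should be followed until radiological progression is documented, irrespective of compliance to treatment, or until the subject enters follow-up".
- Sections 5.3 and 6.5: stopping treatment is not leaving the study, and subjects are followed for one year after treatment or until death. The study calendar shows only survival status in that period.

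The primary endpoint is "Best overall response of CR or PR, as per RECIST 1.1", a proportion in which a subject who progresses without responding counts as a non-responder.

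**The concern.** A competing event is one that removes the chance of the event of interest. Here progression does that: treatment stops, response imaging stops, and follow-up then collects survival only. Death before progression also does it, but is likely to be much rarer. The plan chose a competing-risk method and then named the less common event.

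If death is the only competing code, a subject who progresses without responding is ordinarily censored at the progression scan. The estimator then treats that subject as still able to respond at the rate of those who remain on treatment. The documents give no way for that to happen on the study schedule. The curve would then rise above the proportion who actually responded, and two analysts could draw materially different curves from the same 39 subjects.

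**Working it through.** **The plan's own figures.** The plan gives no figure for time to response. The 7% and 20% used below are the ORR values of the Simon design. That design (stop at ≤1/21, active at ≥6/39) reproduces exactly: type I error 0.0499 at 7% and power 0.805 at 20%.

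**Inputs.**
- Scan interval: 8 weeks = 56/30.4375 = 1.840 months (Section 10.2).
- Median time to progression: 4.6 months. This is the PFS of a cited trial's fulvestrant-plus-placebo arm (Section 1.1), borrowed here for non-responders. It is an assumption; 3 and 6 months are also shown.
- First events of non-responders: 5% deaths, 95% progressions (assumption).
- Response timing: four patterns (assumption).

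**Estimator.** At scan k, with n_k at risk, r_k responses, p_k progressions and d_k deaths:

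F(k) = F(k−1) + S(k−1) × r_k/n_k, and S(k) = S(k−1) × (1 − e_k/n_k).

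- Progression censored: e = r + d; r, p and d leave the risk set.
- Progression competing: e = r + p + d; r, p and d leave.
- Progressors kept at risk: e = r + d; only r and d leave.

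**Expected values.** The monthly hazard is ln 2/4.6 = 0.1507. The fraction of non-responders without an event that survives one interval is exp(−0.1507 × 1.840) = 0.758. At ORR 20% the first interval therefore has 0.80 × 0.242 = 0.194 first events: 0.184 progressions and 0.0097 deaths. With responses spread evenly over five scans (0.04 each) and progressors censored:

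| Scan | At risk | Respond | Progress | Die | S before | F |
|---|---|---|---|---|---|---|
| 1 | 1.0000 | 0.0400 | 0.1840 | 0.0097 | 1.0000 | 0.0400 |
| 2 | 0.7663 | 0.0400 | 0.1395 | 0.0073 | 0.9503 | 0.0896 |
| 3 | 0.5795 | 0.0400 | 0.1057 | 0.0056 | 0.8916 | 0.1511 |
| 4 | 0.4282 | 0.0400 | 0.0801 | 0.0042 | 0.8215 | 0.2279 |
| 5 | 0.3039 | 0.0400 | 0.0607 | 0.0032 | 0.7367 | 0.3248 |

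The true value at scan 5 is 5 × 0.04 = 0.20. Plateaus with progressors censored:

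| Response timing | ORR 20%, median 4.6 mo | ORR 20%, 3 mo | ORR 20%, 6 mo | ORR 7%, 4.6 mo |
|---|---|---|---|---|
| All at scan 1 | 20.0% | 20.0% | 20.0% | 7.0% |
| 70/20/10% at scans 1–3 | 22.4% | 24.1% | 21.8% | 7.9% |
| Even over 3 scans | 25.5% | 29.3% | 24.1% | 9.2% |
| Even over 5 scans | 32.5% | 42.1% | 28.9% | about 12% |

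With progression as a competing event, or progressors kept at risk, every cell returns the true 20% or 7%.

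**Check at n = 39.** In 2,000 simulated trials per scenario (median 4.6 months, 70% or 50% of the remaining responders first responding at each scan), the mean plateau was 22.9% and 26.9% at ORR 20%, and 8.0% and 9.6% at ORR 7%. Both alternative codings gave the observed proportion in every scenario.

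**One data set.** Take 39 subjects, 8 of them responders, over six scans: responses 4, 2, 1, 1, 0, 0; progressions 14, 5, 4, 3, 2, 1; deaths 1, 1, 0, 0, 0, 0. With progressors censored the numbers at risk at the first four scans are 39, 20, 12 and 7, and the increments are 0.1026 + 0.0872 + 0.0618 + 0.0970 = 0.3485. With progression competing they are 0.1026 + 0.0513 + 0.0256 + 0.0256 = 0.205 = 8/39. This is an early-progression case: 15 of the 31 non-responders have left by the first scan.

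**The case against.** The strongest reply is that the plan nowhere says to censor at progression. Subjects off treatment remain in the study, and deaths are sought for a year afterwards. Death as the sole competing event is coherent if progressors stay at risk as non-responders, and the bias is then nil. This stands: the defect is an unstated rule, and a reader who infers that the plan prescribes a biased estimator goes beyond the text. It does not remove the point, because the benign handling is not written down either, and imaging that ends at progression makes censoring there the natural coding.

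A reader might also infer that the secondary curve would undermine the primary ORR. The documents do not support that. ORR rests on its own count rule, and Section 9.2 states that "Point and 95% interval estimate of ORR will be evaluated accounting for possibility of early futility stopping". No test or decision uses the time-to-response curve.

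The size is also open to challenge. Response timing is not given, the 4.6 months describes all patients in another trial's arm, and there is no excess if every response appears at the first scan. That stands too. The upper figures need late responses or early progression and should not be read as typical. Nor should progression be taken to account for every non-responder: on the assumptions above it is 0.80 × 0.95 = 76% of subjects at ORR 20%, before withdrawals and toxicity stops.

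**Conclusion.** The concern holds as an omission with a conditional bias. Section 9.2 leaves out the main event that precludes a documented response and does not say how it is handled. If progressors are censored, with a 4.6-month median and the other assumptions above, the excess at a true ORR of 20% runs from zero to about 13 points (a plateau of 20% to about 33%). At a true ORR of 7% it runs from zero to about 5 points (7% to about 12%). Earlier progression or later responses enlarge it. If progressors are kept at risk, it is zero. The effect is confined to a secondary descriptive endpoint, and the primary test and the 6/39 rule do not change. It is still worth correcting before analysis, because the choice of coding alone can move the curve materially.

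**What to change.** In Section 9.2, replace the clause on death with: *Progression or death without prior response will be competing events; subjects alive without progression or response are censored at the last tumor assessment.* Equivalently, state that subjects who progress without response stay in the risk set as non-responders.

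With complete follow-up the plateau then equals the raw observed response proportion. The ORR estimate adjusted for the two-stage design may still differ slightly, and a table footnote should say so. Subjects who stop imaging without progression, for example after toxicity, would still be censored under the competing-event rule, so their number should be reported.

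The cost is one sentence. Progression dates are already collected for PFS, and no other analysis changes.

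### With about 8 responders expected, the single-predictor ORR models for continuous predictors would be better fitted by Firth-penalised logistic regression than by default maximum likelihood

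*Combined protocol and SAP*

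**What the plan says.** The secondary analyses in section 9.2 say: "Regression analysis will be completed using Cox proportional regression model for PFS and logistic regression model for ORR". No estimation method is given, so ordinary maximum likelihood is an inference from default practice.

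The sample is fixed by the Simon design: "A total of 39 patients will be enrolled, and the study will be conducted in two stages". The trial continues past 21 subjects on this condition: "If ≥ 2 responses were observed, then 18 additional subjects will be enrolled". Success is 6 or more responses in 39.

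The section recognises that the sample is small. A categorical variable is examined only if the number of events ("responses for ORR and progression or death for PFS) is greater than five per category") is reached. It adds "Single-predictor models will be used" and says that "due to a small number of patients we are not expecting to fit multiple regressions". No matching limit is stated for continuous predictors.

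On predictors it says "The impact of the following predictors will be explored: age, race, ER status, PgR status, prior therapy", and then lists number of metastatic sites, measurable disease and biomarkers. It does not say which will be analysed as continuous. Section 10.5.1 has PgR expression reported as a percentage of staining tumour cells and plans to relate its degree to response, so a continuous PgR predictor is plausible. On software: "All planned data analyses will be completed with SAS 9.4".

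**The concern.** Maximum-likelihood logistic regression with very few events gives log odds ratios that are, on average, too far from zero when a real effect exists, with a long upper tail. The plan guards against sparse data for categorical predictors, and that guard will remove nearly all of them from the ORR analysis at the planned response rate. What remains is the set of continuous predictors, such as age, number of metastatic sites, PgR percentage and marker levels, where nothing limits the problem.

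At stake is the reported size of any association between these predictors and response. The degree of PgR expression matters most here, because the receptor is the drug's target and the trial enrols both PgR-positive and PgR-negative disease.

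**Working it through.** **1. The plan's own design figures.** Inputs from 9.2: 21 then 18 subjects; continue at 2 or more responses; success at 6 or more of 39; ORR 7% and 20%. The probability of success is the sum over x = 2 to 21 of P(X1 = x; 21, p) × P(X2 ≥ 6 − x; 18, p). This gives 0.0499 at 7% and 0.805 at 20%, which reproduces the stated 5% and 80%.

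**2. Number of responders.** Expected at ORR 20%: 39 × 0.20 = 7.8. For a binomial with n = 39 and p = 0.20, P(6 to 8) = 0.44, P(6 or more) = 0.82, and so P(9 or more) = 0.82 − 0.44 = 0.38. The range from 6 (the success threshold) to 8 (the rounded expectation) is a fair planning range, though not a majority outcome.

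**3. What the event-count rule lets through.** More than five responses in each of two categories means at least 6 + 6 = 12 responders. P(12 or more of 39) is 0.074 at ORR 20% and 0.253 at 25%. For a 50/50 factor unrelated to response, the chance of meeting the rule at ORR 20% is 0.027. With 6 to 8 responders no two-level factor can meet it.

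**4. Bias for a continuous predictor.** The documents give no effect sizes or predictor distributions, so these are assumptions: one standard-normal predictor, n = 39, marginal ORR 20%, 6 to 8 responders, and true odds ratios of 1, 1.5, 2 and 3 per SD. There were 4,000 simulated data sets per scenario. Maximum likelihood (ML) maximises log L; Firth maximises log L + ½ log |I(β)|. Relative bias = (mean log OR − true log OR) / true log OR. RMSE = √(bias² + SD²).

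| True OR (log) | ML mean log OR, SD | ML bias | ML RMSE | Firth mean log OR, SD | Firth bias | Firth RMSE |
|---|---|---|---|---|---|---|
| 1 (0) | −0.009, 0.495 | none | 0.50 | −0.007, 0.434 | none | 0.43 |
| 1.5 (0.405) | 0.473, 0.557 | 0.068/0.405 = 17% | 0.56 | 0.414, 0.469 | 0.009/0.405 = 2% | 0.47 |
| 2 (0.693) | 0.806, 0.617 | 0.113/0.693 = 16% | 0.63 | 0.700, 0.510 | 0.007/0.693 = 1% | 0.51 |
| 3 (1.099) | 1.306, 0.771 | 0.207/1.099 = 19% | 0.80 | 1.118, 0.597 | 0.019/1.099 = 2% | 0.60 |

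Exponentiating the mean log OR, ML gives 2.24 for a true 2 and 3.69 for a true 3; Firth gives 2.01 and 3.06. A separate run gave ML 2.22 and 3.60 and Firth 2.01 and 2.99, with RMSE 0.58 against 0.49 and 0.74 against 0.56. For ML that is ln(2.22/2)/ln 2 = 15% and ln(3.60/3)/ln 3 = 17%. Separated data sets, excluded from the ML averages, were at most 0.05%, too few to matter.

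**5. Median odds ratios, same conditions.** True 2: ML 2.09, Firth 1.91. True 3: ML 3.33, Firth 2.85. On this scale ML is slightly high and Firth slightly low.

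**The case against.** The strongest reply is that these are exploratory models whose inference already holds. Wald interval coverage is 96-98% under both methods. At true OR 2 the ML bias is 0.113/0.617 = 0.18 of one standard deviation of the estimate, so noise dominates. ML and Firth estimates have a rank correlation of 0.999, so the ordering of equally scaled markers hardly depends on the choice. The plan also contains no error: a Firth fit is still logistic regression. All of this stands, and it makes the point an improvement rather than a correction.

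A reader might infer more, in four ways that are not supported.

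- **That every ORR odds ratio is overstated.** Categorical predictors are essentially not fitted at 6 to 8 responders. For binary predictors that meet the event-count rule (simulated at ORR 30%), the bias runs toward 1: ML gives 1.43 for a true 2 and 1.72 for a true 3. That comes from selection by the rule, and Firth (1.40 and 1.68) does not repair it.
- **That ML creates false leads.** At a true OR of 1 it is unbiased, and its Wald test rejects in 3.5% of data sets, below the nominal 5%. Estimates beyond 4-fold fall from about 1.3-1.5% to 0.7% with Firth, a small gain.
- **That these models choose markers for phase III.** Section 9.2 ties the phase III decision to 6 or more responses in 39 and describes the predictors only as explored.
- **That the change is free of drawbacks.** Firth puts the median odds ratio slightly low and draws fitted probabilities toward one half.

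**Conclusion.** The point holds as a low-priority improvement, limited to ORR models with predictors analysed as continuous. There, default maximum likelihood makes a real effect look larger on average, by about 15-19% on the log scale at true odds ratios of 2 to 3 per SD. Firth reduces this to about 1-2% and lowers RMSE at OR 2 from about 0.58-0.63 to 0.49-0.51. The primary ORR decision and its interval are untouched.

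The sizes rest on a standard-normal predictor, 6 to 8 responders, the chosen odds ratios, and reading the plan's unspecified estimator as maximum likelihood. A skewed predictor such as PgR percentage could give different figures. Coverage was examined for Wald intervals only, not for the profile intervals recommended below.

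**What to change.** Add to the secondary analyses in 9.2: *Single-predictor ORR models with a predictor analysed as continuous will be fitted by Firth-penalised logistic regression with profile penalised-likelihood 95% confidence intervals, and reported as exploratory.* List which predictors will be treated as continuous, and note that at the planned response rate the event-count rule will in practice exclude categorical predictors from the ORR models. Use the fit for odds ratios, not for predicted response probabilities.

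The cost is a few lines of text, agreed before results are seen, with no extra patients or data. The plan names SAS 9.4; that its logistic procedure offers a Firth option is general software knowledge, not something the documents state.
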